11.6 Reporting of Serious Adverse Events

11.6.1 Reporting period

All events that meet one or more criteria of seriousness that occurred **from the time the patient's signed informed consent up to 110 days after the last study drug administration**, regardless the relationship to the study treatment requires the completion of an SAE Report Form in addition to being recorded on the AE page of the eCRF.

A Serious Adverse Event that occurs after this time, including during the follow-up period, **if considered related to the study medication**, will be reported regardless of the time between the last drug administration and the event onset.

11.6.2 Obligations of the Investigator

The Investigator is required to ensure that the data on these forms is accurate and consistent. This requirement applies to all SAEs (regardless of relationship to study drugs) that occur during the study (from the time the patient signs informed consent to 110 days after the last dose of study drug(s)), and those made known to the Investigator at any time thereafter that are considered to be related study drugs.

All serious adverse events that have not resolved by the end of the study, or that have not resolved upon discontinuation of the subject's participation in the study, must be followed until any of the following occurs:

- The event resolves
- The event stabilizes
- The event returns to baseline, if a baseline value/status is available

- The event can be attributed to agents other than the study drug or to factors unrelated to study conduct
- It becomes unlikely that any additional information can be obtained (subject or health care practitioner refusal to provide additional information, lost to follow-up after demonstration of due diligence with follow-up efforts)

Additionally, any serious adverse event, considered by an investigator who is a qualified physician to be related to MSD product that is brought to the attention of the investigator at any time following consent through the end of the specified safety follow-up period specified in the paragraph above, or at any time outside of the time period specified in the previous paragraph also must be reported immediately according to SAE reporting requirements mentioned above. Events concerning secondary malignancy need to be reported during follow-up period regardless of causality.

All participants with serious adverse events must be followed up for outcome.

In case of serious adverse events, AESI and special situations **the Investigator must immediately report by sending the scanned and signed the SAE form to:**

[REDACTED]

Recipients: ZKS and CTO (Ulm)

All SAE forms must be dated and signed by the responsible Investigator or one of his/her authorized staff Members.

- The SAE report should provide a detailed description of the SAE specifying the date of onset, severity, action taken regarding trial medication, corrective therapy given, outcome of all serious adverse events and his opinion as to whether the serious adverse event can be related to the study drugs. Whenever possible, symptoms should be grouped as a single syndrome or diagnosis.
- Information about results of any examinations carried out including laboratory tests that are important for the diagnosis, assessment, or treatment of a SAE and the dates on which these examinations were performed should be given within the SAE form. For laboratory tests the respective normal reference range should be provided as well.
- Information for final description and evaluation of a case report may not be available within the required time frames for reporting outlined above. Nevertheless, for regulatory purposes, initial reports should be submitted within the prescribed time as long as the following minimum criteria are met: an identifiable patient; a suspect medicinal product; an identifiable reporting source (the identity of the Investigator: name, address, site number and email/telephone number); an event or outcome assessed as reportable;

investigator causality assessment (in case the investigator causality is missing, the causality will be considered related and the case may qualify as a SUSAR). Follow-up information should be actively sought and submitted as it becomes available.

- Additional information to any SAE should be provided by the investigator on a subsequent SAE-Report Follow up form and sent by e-mail to Sponsor/ZKS as soon as they become available, but not later than 3 days. If a subject died and an autopsy has been performed, copies of the autopsy report and death certificate are to be sent as soon as these become available. A translation of the autopsy report and death certificate into English language has to be provided, if written in a language other than English or German.
- For the time period beginning at treatment allocation through 110 days following cessation of treatment, or 30 days following cessation of treatment if the participant initiates new anticancer therapy, whichever is earlier, any serious adverse event, or follow up to a serious adverse event, including death due to any cause whether or not related to the MSD product, must be reported within 24 hours to the Sponsor and by the Sponsor within 1 working day to MSD Pharmacovigilance Germany [REDACTED]
[REDACTED]

Where required by local regulation, the Investigator is responsible for informing the IRB/EC of the SAE and providing them with all relevant initial and follow-up information about the event. The Investigator must keep copies of all SAE information on file including correspondence with the Sponsor/ZKS and the IRB/EC.

11.6.3 Safety Queries

Queries pertaining to SAEs will be communicated from the Sponsor/ZKS to the site via facsimile or electronic mail. The response time is expected to be no more than 1 calendar day (urgent queries) or three (3) business days (non-urgent queries). Urgent queries (e.g., missing causality assessment) may be handled by phone.

11.6.4 Obligations of the sponsor

SAE reports and any other relevant safety information must be reported from the Sponsor to MSD Pharmacovigilance Germany [REDACTED] [REDACTED] [REDACTED] [REDACTED] [REDACTED] within 1 working day after becoming aware by the Sponsor if it causes the participant to be excluded from the trial, or is the result of a protocol-specified intervention, including but not limited to washout or discontinuation of usual therapy, diet, placebo treatment or a procedure. It has to be reported by facsimile, or other appropriate

method, using the SAE Report Form. This instruction pertains to initial SAE reports as well as any follow-up reports.

During the course of the study, the Sponsor will report in a pseudonymized, expedited manner all SAEs that are both unexpected and suspected to be related to study drugs, to the Competent Authorities, concerned Ethic Committees in each country in accordance with international and local regulations, and to the Investigators:

- within 7 days of first knowledge by the sponsor of such a case for fatal or life-threatening events. Relevant missing information for fatal or life-threatening cases will be subsequently submitted within an additional eight days
- and within 15 days of first knowledge by the sponsor for other serious adverse events.

The expectedness of an adverse reaction will be determined by the Sponsor according to the reference safety information (e.g. Investigator's Brochure or SmPC) of the trial medication.

Expedited reporting (SUSAR, New Safety Issues) and submission of Development Safety Update Reports to the relevant Competent Authorities and to the Ethics Committees according to local regulation will be performed by ZKS Ulm and CTO.

11.7 Product quality complaint handling

A product quality complaint (PQC) is defined as any suspicion of a product defect related to manufacturing, labeling, or packaging, i.e., any dissatisfaction relative to the identity, quality, durability, or reliability of a product, including its labeling or package integrity. A PQC may have an impact on the safety and efficacy of the product. Timely, accurate, and complete reporting and analysis of PQC information from studies are crucial for the protection of subjects, investigators, and the sponsor, and are mandated by regulatory agencies worldwide. All initial PQCs of an IMP must be reported to Sponsor/ZKS by the study-site personnel within 24 hours after being made aware of the event. The sponsor is responsible to report the PQC to either MSD Pharmacovigilance Germany or Pharmacovigilance Mundipharma [REDACTED]

[REDACTED] (depending on the IMP concerned). If the defect is combined with a serious adverse event, the investigational staff must report the PQC to Sponsor/ZKS according to the serious adverse event reporting timelines. A sample of the suspected product if possible should be maintained for further investigation.

11.8 Benefit/Risk assessment of treatment program

MZL is a subtype of cancer with a normally indolent clinical course. Despite this the disease is life threatening and leads to continuous deterioration of the patient's clinical situation without

adequate treatment. In this trial only patients will be included who are in need of treatment for whom local therapy is not feasible, for whom local therapy did not result in disease control or who relapsed after systemic treatment. In this situation the treatment program with Pembrolizumab/Rituximab represents a chemo-free approach, which promises high efficacy without major toxicity. The assumption of high efficacy is based on the experience with Pembrolizumab single agent in partly heavily pretreated relapsed/refractory B-Non-Hodgkin's lymphoma and on experience with Pembrolizumab in combination with Rituximab in relapsed follicular lymphoma, demonstrating high efficacy and clinically manageable toxicity. In addition, there is a large body of evidence, that Rituximab single agent is well tolerated and has anti-lymphoma activity in patients with MZL. Adequate pre-medication is obligatory in this trial and there will be close monitoring for toxicity of the first 6 patients included. Taken together, the risk for the patients to experience unexpected serious toxicity will be low and has to be balanced with the high likelihood to receive a chemo-free treatment, which will allow disease control for a longer time period, thereby delaying the need for the patient to accept more dose intense chemotherapy. Thus, the benefit of the treatment program is expected to be superior to the potential short and long term toxicities.

12. Statistical Considerations

12.1 Expected Improvement

In MZL a variety of treatment modalities are used such as Rituximab single agent, chemotherapy or Rituximab in combination with chemotherapy. It is widely accepted that in this non-curative indolent B – cell lymphoma of the mostly elderly patient chemotherapy – related toxicity should be avoided and that chemotherapy-free approaches are highly attractive in this patient population. So far Rituximab single agent is the most frequent chemotherapy-free approach used in this entity. Thus, a novel chemotherapy – free treatment approach should be at least as efficient as Rituximab monotherapy. In a large randomized study Rituximab single agent therapy induced a CRR of 55.8% compared to 78.8% for the combination of Rituximab and chlorambucil in de novo MZL of the MALT type¹. CR rates in splenic MZL are comparable high at about 60%^{8,11}, whereas patients with nodal MZL achieve a CRR of around 20%⁹. As the distribution of subtypes is about 70% MALT, 20% splenic, and 10% nodal MZL, a CRR which is better than 56% for the total population with MZL should at least be achieved by a new chemotherapy – free approach after end of treatment (18 cycles after start of therapy) for such a mixture of the population.

The goal of this study is to test the efficacy of the chemotherapy - free combination Pembrolizumab/Rituximab in treatment – naïve and relapsed symptomatic MZL aiming at achieving comparable treatment results compared to immuno- chemotherapy.

12.2 Sample Size

For sample size calculation the one-sided one sample exact binomial test was used. According to the above data, the CRR for the total group of the different subtypes of MZL must be better than 56% after end of treatment (18 cycles). Anticipating a CRR for Pembrolizumab/Rituximab of about 75%, a significance level of 2.5% (because of one-sided test) and a power of 80%, 48 full evaluable patients will be necessary to show that the combination will be a promising candidate for challenging immuno-chemotherapy (PROC POWER, SAS 9.3; 48 patients is the first number of patients with a stable power of more than 80%). It is expected, that the rate of withdrawal in the study is smaller than 15%. According to these parameters, the study will enrol 56 subjects. The distribution between the sexes is not relevant, because neither incidence of MZL is differed between sexes nor clinically outcome measures such as response, progression free and overall survival has been shown to be related to sexes.

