
Statistical Methods
	
In MZL a variety of treatment modalities are used such as Rituximab single agent, chemotherapy or Rituximab in combination with chemotherapy. It is widely accepted that in this non-curative indolent B – cell lymphoma of the mostly elderly patient chemotherapy – related toxicity should be avoided and that chemotherapy-free approaches are highly attractive in this patient population. So far Rituximab single agent is the most frequent chemotherapy-free approach used in this entity. Thus, a novel chemotherapy – free treatment approach should be at least as efficient as Rituximab monotherapy. In a large randomized study Rituximab single agent therapy induced a CRR of 55.8 % compared to 78.8 % for the combination of Rituximab and chlorambucil in de novo MZL of the MALT type. CR rates in splenic MZL are comparable high at about 60%⁸, whereas only 10% of patients with nodal MZL achieve a CRR of around 20%⁹: As the distribution of subtypes is about 70% MALT, 20% splenic, and 10% nodal MZL, a CRR which is better than 56% should at least be achieved by a new chemotherapy – free approach after end of treatment (18 cycles) for such a mixture of the population.
 
The goal of this study is to test the efficacy of the chemotherapy - free combination Pembrolizumab/Rituximab in treatment – naïve and relapsed symptomatic MZL aiming at achieving comparable treatment results compared to immuno- chemotherapy.
 
Sample size/Power Calculation: For sample size calculation the one-sided one sample exact binomial test was used. According to the above data, the CRR must be better than 56% after end of treatment (18 cycles). Based on a CRR for Pembrolizumab/Rituximab of about 75%, a significance level of 2.5% (because of one- sided test) and a power of 80%, 48 full evaluable patients will be necessary to show that the chemo-free combination will be a promising candidate for challenging immunochemotherapy (SAS PROC POWER, SAS 9.3; 48 patients is the first number of patients with a stable power of more than 80%). It is expected, that the rate of withdrawal in the study is smaller than 15%. According to these parameters, the study will enroll a maximum of 56 subjects.
 
Statistical analysis of primary and secondary endpoints: The primary parameter CRR will be evaluated in an intention to treat way after end of treatment (18 cycles), which means that all eligible patients who received at least one cycle of treatment will be included in the analysis of the primary endpoint (Core Analysis Population). Only patients who withdraw will be excluded from this analysis population (about 15%). This analysis population consists of all eligible patients included in the study who received at least one cycle of treatment. Patients without staging at regular end of treatment will be defined as non-responder (i.e. CR='NO'). The one sample exact binomial test will be used for the analysis of the primary endpoint to test the CRR against the fixed value 56% at the 2.5% significance level (one-sided). Thus, the decision about the new concept will be based on a statistical test of the form:
 
HA : { CRR > 56%} vs. H0: { CRR ≤ 56%}
 
Thus, claim of success can be done if 36 (75% of 48 patients) or more complete responders (patients with CR) will be observed. Patients who withdraw will be included in a separate explorative analysis. Additionally, a one-sided 97.5% confidence interval for CRR will be calculated as an effect estimator. Exploratory use of univariate logistic regression models will be used to investigate the influence of putative risk factors associated with CRR. All secondary endpoints will be analyzed exploratory by respective descriptive analysis and 95%-confidence intervals.

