12.3 Analysis of the Primary Endpoint

The primary endpoint (CRR) will be evaluated after end of treatment (18 cycles) after the last recruited patient has started her/his treatment. The primary parameter CRR will be evaluated in a modified intention to treat way, which means that all patients for whom the primary endpoint CRR is measured after end of treatment will be included in the analysis of the primary endpoint (Core Analysis Population, see subsection 12.6). Only patients who withdraw will be excluded (about 15% are expected). The one sample exact binomial test will be used for the analysis of the primary endpoint to test the CRR against the fixed value 56% at the 2.5% significance level (one-sided). Thus, the decision about the new concept will be based on a statistical test of the form:

HA: {CRR > 56%} vs. H0: {CRR ≤ 56%}

Thus, claim of success can be done if 36 (75% of 48 patients) or more responders (patients with CR) will be observed. Patients who withdraw will be included in a separate explorative analysis. Additionally, a one-sided 97.5% confidence interval for CRR will be calculated as an effect estimator. Exploratory use of univariate logistic regression models will be used to investigate the influence of putative risk factors associated with CRR.

Subgroup analyses in the subtype (MALT lymphoma, splenic MZL, nodal MZL) will be performed as further exploratory analyses.

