2.2 Biometrical Report

Results of statistical analysis (e.g. tables, figures, and summary statistics) will be provided to the Comprehensive Cancer Center / Department of Internal Medicine III / Institute of Experimental Cancer Research for preparation of the Synopsis according to the ICH E3 guideline (CPMP/ICH/137/95, July 1996). All outputs will be provided in English language (e.g. title of tables, listings or figures, names of variables in listings and tables). A separate biometrical report will not be provided.

3 Changes in the Conduct of the Study or Planned Analyses

The trial was stopped after recruiting of 22 of 56 planned patients because of delayed recruitment. Due to the small sample sizes, the exploratory use of univariate logistic regression analysis to investigate the influence of putative risk factors associated with CRR will not be done due to expected problems in model fitting. Likewise, the planned subgroup analyses for the MZL subtype strata MALT lymphoma, splenic MZL, nodal MZL will not be performed because summary statistics (e.g. mean, standard deviation, percentages) would be not meaningful. Instead, a simple description of the patients in the three subgroups will be provided (e.g. number of patients, time course, primary and secondary endpoints). No other deviations from the study protocol are known at time of finalizing this plan.

4 Analysis Sets

Core Analysis Population: As this study is a trial with only one treatment arm, all analyses will be performed only for one analysis population, the Core Analysis Population. This analysis population consists of all eligible patients included in the study who received at least one cycle of treatment. Patients without staging at regular end of treatment will be defined as non-responder (i.e. CR='NO'). Only patients who withdraw will be excluded from this analysis population (about 15% were expected). The results on efficacy in the Core Analysis Population were considered to be the main efficacy results (confirmatory results).

Safety Population: The safety population and the Core Analysis Population are identical in this trial.

5 Definitions

The following notation will be used in this SAP:

- the ***bold and italic marked word*** specify the data table in the SAS data base
- the *italic marked word* signs a variable or a value of a variable in the SAS data base

Primary endpoint:

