8.2.2 Sample Size Calculation

Full details of the sample size calculation are in the CTP at pages 13 and 92.

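### With the stated exact test against 56%, 48 patients give 69.9% power, not over 80%; the 36-CR success rule gives 57.7%; neither is restated for the 22 patients enrolled

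*Protocol*

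**What the plan says.** Protocol 12.2 names the method: "For sample size calculation the one-sided one sample exact binomial test was used". It assumes a CRR of about 75% with "a significance level of 2.5% (because of one-sided test) and a power of 80" per cent, arrives at 48 evaluable patients, and justifies that number with the remark that "48 patients is the first number of patients with a stable power of more than 80" per cent. Allowing for fewer than 15% withdrawals, it plans to enrol 56.

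Protocol 12.3 fixes the null. The exact test is used "to test the CRR against the fixed value 56% at the 2.5% significance level (one-sided"). It then concludes that "claim of success can be done if 36 (75% of 48 patients) or more responders (patients with CR) will be observed". The Statistical Methods part of the Synopsis gives the same threshold: "claim of success can be done if 36 (75% of 48 patients) or more complete responders".

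SAP 8.2.1 keeps the exact test against 56% at one-sided 2.5% and describes the result as confirmatory. It does not carry over the 36-CR sentence. On sample size, SAP 8.2.2 says only: "Full details of the sample size calculation are in the CTP at pages 13 and 92". SAP section 3 reports: "The trial was stopped after recruiting of 22 of 56 planned patients because of delayed recruitment". It drops the logistic regression and the subgroup analyses because of the small numbers and says that no other deviations are known. It gives no critical value or power for the reduced sample.

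**The concern.** The protocol states every input needed to check the power, and 36 of 48 is exactly 75%, the rate assumed under the alternative. A design whose success threshold equals its expected count has power not far above one half, so a threshold of 36 and power above 80% cannot both be right.

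Two things are at stake. The protocol contains two decision rules that can disagree on the same data. And the only power figure on record for the confirmatory test exceeds 80%, which the design did not have even at full size and which is far from the truth at 22 patients. A non-significant result could then be read as a well-powered negative finding.

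**Working it through.** **Inputs.** Null 0.56 (Protocol 12.3); alternative 0.75, one-sided level 0.025, 48 evaluable, 56 enrolled (Protocol 12.2); success at 36 CRs (Protocol 12.3 and Synopsis); source rate 55.8% behind the rounded null (Protocol 12.1); 22 enrolled (SAP section 3).

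**Formula.** For n patients and threshold r, the tail is P(X ≥ r | n, p) = Σ C(n,k) p^k (1−p)^(n−k), summed over k = r to n. The critical value is the smallest r whose tail at the null is at most 0.025. Power is the tail at 0.75 for that r.

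**Step 1: the stated design at n = 48.**

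| Threshold | Level at 0.56 | Power at 0.75 | Status |
|---|---|---|---|
| 34 | 0.0255 | 80.0% | exceeds 0.025, not allowed |
| 35 | 0.0120 | 69.9% | critical value of the stated test |
| 36 | 0.0052 | 57.7% | written success rule |

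The stated power above 80% does not reproduce.

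**Step 2: where 48 probably comes from.** With a null of 0.558, 34 CRs give a level of 0.0239, which is allowed, and power is 80.01%. In that case 48 is the first n at or above 80%.

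**Step 3: stability.**
- With a null of 0.558, power falls to 77.5% at n = 49 and 74.8% at n = 50. It stays at or above 80% only from n = 54.
- With the stated null of 0.56, power first reaches 80% at n = 51 (36 CRs, level 0.0236, power 81.5%). It stays there only from n = 57 (40 CRs, level 0.0202, power 84.0%).
- If all 56 planned patients had been evaluable, power would have been 78.3% (40 CRs, level 0.0130).

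**Step 4: conflict between the rules.** A result of 35/48 has one-sided p = 0.0120. It rejects the null but falls short of 36.

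**Step 5: the sample that exists.** The number analysed after withdrawals is not given. The range 17 to 22 is an assumption; 15% withdrawal would leave 22 × 0.85 = 18.7, about 19.

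| Analysed n | CRs needed | Observed rate needed | Level at 0.56 | Power at 0.75 |
|---|---|---|---|---|
| 22 | 18 | 81.8% | 0.0107 | 32.3% |
| 21 | 17 | 81.0% | 0.0158 | 36.7% |
| 20 | 16 | 80.0% | 0.0233 | 41.5% |
| 19 | 16 | 84.2% | 0.0097 | 26.3% |
| 18 | 15 | 83.3% | 0.0148 | 30.6% |
| 17 | 14 | 82.4% | 0.0224 | 35.3% |

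Every threshold lies above the hoped-for 75%. Power rises and falls with n because the binomial is discrete, so no single n represents the range. A rule of 36 CRs cannot be met with 22 patients.

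**The case against.** The strongest reply is that the 48-patient analysis will never be run. The trial stopped at 22, and the SAP's p-value rule sets its own critical value for whatever number is analysed. The test is valid and executable, and type I error is controlled. This stands, and it means that the planned size can no longer be repaired. It does not cover the SAP's reference back to the faulty calculation, or the absence of any cut-off or power for the test it still calls confirmatory.

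Second, the SAP omits the 36-CR sentence, so the conflict between 35 and 36 is not in the current analysis text, and 57.7% describes the protocol's rule only. That is correct. But the omission is not listed in SAP section 3, so a reader holding both documents does not know which rule governs.

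Third, the 36-CR sentence can be read as a sufficient condition, and 36/48 is indeed significant (p = 0.0052). On that reading the 57.7% does not apply, but 69.9% does. Either way the threshold errs on the conservative side.

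Fourth, the error is narrow: rounding 55.8% to 56% moves the level at 34 CRs from 0.0239 to 0.0255, and discreteness does the rest. This explains the figure of 48 but does not make it right, because the plan tests the fixed value 56%, and power at 48 is not stable under either null.

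Finally, nothing in the SAP says that a non-significant result will be read as absence of benefit. That is fair; the harm is a risk of misreading. The SAP discloses the shortfall and provides a confidence interval, which reduces the risk.

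**Conclusion.** The plan is wrong as written. With its own inputs, 48 patients give 69.9% power, about 10 percentage points below the claim. The written threshold of 36, taken as the rule, gives 57.7%, about 22 points below. These figures rest only on the stated null, alternative, level and test. For the trial as conducted, power at a true CRR of 75% is 32.3% if all 22 are analysed and between 26% and 41% for 17 to 22 analysed. With all 22 analysed, a regimen that achieved the hoped-for 75% would therefore fail the test about two times in three (1 − 0.323 = 0.677). The p-value and confidence interval remain valid; what is wrong is the stated power and the stated success threshold.

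**What to change.** Make the correction in the SAP and leave the protocol as the historical record.

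- **SAP section 3:** state that the protocol's threshold of 36 CRs is superseded, that it was not the critical value of the exact test, and that it cannot be reached with 22 patients.
- **SAP 8.2.1:** name an exact one-sided p-value of at most 0.025 against 56% as the sole success criterion. Both documents already specify this test, so no threshold is being relaxed for the actual sample. Give the cut-off for each plausible analysed number, as in the last table above.
- **SAP 8.2.2:** say that the planned 48 patients give 69.9% power against 56%, that the 80% figure corresponds to a null of 55.8%, and that power at the reduced size is about 26% to 41% for 17 to 22 analysed (32.3% at 22). Add that failure to reject is not evidence of no benefit and that the estimate and its confidence interval should carry the interpretation.

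Date the change and record whether the response data were already known. The cost is wording and corrected figures, with no new patients, data or analyses. The stated power becomes less favourable.
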